10.4 Demographic and Other Baseline Characteristics

Demographic and baseline characteristic data will be summarized for each study group and overall. Descriptive statistics (N, mean, standard deviation, median, minimum, and maximum) will be presented for continuous variables. The number and percentage of subjects in each category will be presented for categorical variables. No formal testing of demographic or baseline characteristics will be performed.

10.5 Safety Evaluation

All safety assessments, including AEs, PEs, VS and clinical laboratory evaluations, where indicated, will be presented using descriptive statistics for each study group of UB-612. Data will be summarized for each study group.

Local Reactions and Systemic Events

Local reactions and systemic events recorded on e-diary will be summarized by the severity grading scales by study groups. Numbers and percentages of subjects experiencing each local reaction/systemic event will be presented for each symptom severity by study groups. Summary tables showing the occurrence of any local reactions and occurrence of any systemic event will also be presented.

Unsolicited Adverse Event

This analysis applies to all unsolicited adverse events occurring during the study, recorded in AE eCRF, with a start date on or after the date of vaccination. Unsolicited AEs occurring during the study will be coded using the most recent version of Medical Dictionary for Regulatory Activities (MedDRA). The adverse events will then be grouped by MedDRA preferred terms into frequency tables according to system organ class.

All reported unsolicited adverse events, as well as adverse events judged by the investigator as at least possibly related to study vaccine, will be summarized according to system organ class and preferred term within system organ class. When an unsolicited adverse event occurs more than once for a subject, the maximal severity and strongest relationship to the study group will be counted.

Separate summaries will be produced for the following categories, such as serious adverse events and unsolicited AEs related to vaccinations will be presented. Data listings of all unsolicited adverse events will be provided by subject.

Physical Examination

All physical examination findings will be listed and summarized by time point and study group. Shift table will be also presented, if appropriate.

Vital Signs

All vital sign findings will be listed and summarized by time point and study group.

Laboratory Evaluations

Laboratory safety data will be analysed descriptively by time point and study group. Shift table for laboratory data will be shown by visit using categorization of laboratory according to local laboratory's normal reference range.

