6.2 Primary Endpoints

- Occurrence of adverse reaction within 7 days after vaccination
 - * Adverse reaction is defined as post-vaccination solicited adverse event, and unsolicited adverse event which is related to study vaccine.
- The percentage of subjects with \geq Grade 3 adverse events within 7 days after vaccination

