3. Unsolicited adverse events were reported by 85.0% subjects in UB-612 vaccine 10 µg group, 60.0% subjects in UB-612 vaccine 30 µg group, and 35.0% subjects in UB-612 vaccine 100 µg group. Most of unsolicited adverse events was judged as Grade 1 and 2. Blood pressure diastolic increased in 2 subjects and blood pressure ambulatory increased in 1 subject in UB-612 vaccine 10 µg group, and blood pressure diastolic increased in 1 subject in UB-612 vaccine 30 µg group, were reported as Grade 3. No \geq Grade 3 unsolicited adverse events was found in UB-612 vaccine 100 µg group.
4. Due to procedural issues, some local reactions at the vaccination sites were recorded in the AE eCRF as unsolicited events and were not reported in the subject e-diary as solicited events. The related-vaccine unsolicited AEs were found in 50.0%, 15.0%, and 5.0% subjects in UB-612 vaccine 10, 30 and 100 µg group, respectively. The frequently related unsolicited adverse events related to vaccine were injection site reaction (6 subjects, 30.0%) and malaise (5 subjects, 25.0%) in UB-612 vaccine 10 µg group. The injection site rash, alanine

aminotransferase increased, haemoglobin decreased, which were reported as the related unsolicited adverse events in each 1 subjects in UB-612 vaccine 30 µg group. Constipation in 1 subjects was judged as related unsolicited adverse events in UB-612 vaccine 100 µg group.

5. No deaths, and no serious adverse events reported was found in this study till now. No clinically significant change in the physical examination or ECG measurement in this trial was noted.

The immune responses in antigen-specific antibody and neutralizing antibody could be observed at Day 28 and could achieve 4-fold increase in the majority of 10, 30, and 100 µg vaccine group at Day 42 and 56.

1. All subjects in UB-612 vaccine 10, 30 and 100 µg group revealed no detection in antigen-specific antibody before vaccination. In UB-612 vaccine 10 µg group, GMT increased to 350.79 at Day 42 (14 days after second vaccination) and 526.98 at Day 56 (28 days after second vaccination). In UB-612 vaccine 30 µg group, GMT increased to 366.80 at Day 42 and 269.06 at Day 56. In UB-612 vaccine 100 µg group, GMT increased to 2240.15 at Day 42 and 805.11 at Day 56.

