9.5.6.6 Assessment of Severity

All AEs, except AEs in e-diary card, will be assessed according to the US NCI Common Terminology Criteria for Adverse Events (CTCAE) 5.0 (published on November 27, 2017) associated with the AE term. The following standard with 5 grades is to be used to measure the severity of adverse events in this study.

Table 9-7 Intensity scales of AE

Grades of AE	Description
Grade 1	Mild; asymptomatic or mild symptoms; clinical or diagnostic observations only; intervention not indicated.
Grade 2	Moderate; minimal, local or noninvasive intervention indicated; limiting age-appropriate instrumental ADL*
Grade 3	Severe or medically significant but not immediately life-threatening; hospitalization or prolongation of hospitalization indicated; disabling, limiting self care ADL**
Grade 4	Life-threatening consequences; urgent intervention indicated.
Grade 5	Death related to AE.

* Instrumental activities of daily living (ADL) refer to preparing meals, shopping for groceries or clothes, using the telephone, managing money, etc.

** Self-care ADL refer to bathing, dressing and undressing, feeding self, using the toilet, taking medication, and not bedridden.

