9.5.8 Communication and Use of Technology

This study may employ various methods, such as e-dairy, telephone, or other communication pathway, to contact with participants for record and maintain the study information. The communication items include but not limited to:

- Record 7-day solicited symptoms and 14-day skin allergic reaction after vaccination in reactogenicity e-diary
- Record unsolicited AEs or/and symptoms of COVID-19 on Day 8, Day 15, Day 22, Day 36, Day 43, Day 64, Day 71, Day 78, Day 85, **the day on 7 days after Visit 6 (only for subjects receiving 3rd dose)**, Day 253, and Day 309 using telephone communication
- Record regular surveillance for COVID-19 illness in e-dairy. A prompt on their smartphone device to regularly surveillance for signs and symptoms of COVID-19 every week after Day 57. If any potential symptoms for COVID-19 illness is reported, a telephone call will be made between site staffs and subjects.
- Unscheduled visit set-up or visit reminders

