10.5.1 Analysis of Primary Safety Endpoint(s)

- Local reactions for up to 7 days following each dose

Local reactions for up to 7 days following each dose will be summarized with counts and percentages of participants with the indicated endpoint and the associated Clopper-Pearson 95% CIs by study group and each vaccination. The group comparison will be assessed by Fisher's exact test. Summary of descriptive statistics by age group will be also provided.

- Systemic events for up to 7 days following each dose

Systemic events for up to 7 days following each dose will be summarized with counts and percentages of participants with the indicated endpoint and the associated Clopper-Pearson 95% CIs by study group and each vaccination. The group comparison will be assessed by Fisher's exact test. Summary of descriptive statistics by age group will be also provided.

- Unsolicited AEs from Day 1 to Day 57

Unsolicited AEs will be presented by descriptive summary statistics (counts, percentages, and associated Clopper-Pearson 95% CIs) with system organ class and preferred term for each study group. The group comparison will be assessed by Fisher's exact test. Summary of descriptive statistics by age group will be also provided.

- MAAEs and SAEs from Day 1 to Day 365

MAAEs and SAEs will be summarized by counts, percentages, and associated Clopper-Pearson 95% CIs for each study group. The group comparison will be assessed by Fisher's exact test. Summary of descriptive statistics by age group will be also provided. **Additionally, the AESIs and ADEs occurred after third vaccination for subjects received three vaccinations will be also summarized separately.**

- AESIs and ADEs from Day 1 to Day 365

AESIs and ADEs will be summarized by counts, percentages, and associated Clopper-Pearson 95% CIs for each study group. The group comparison will be assessed by Fisher's exact test. Summary of descriptive statistics by age group will be also provided. **Additionally, the AESIs and ADEs occurred after third vaccination for subjects received three vaccinations will be also summarized separately.**

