10.9 Interim Analysis

Six interim analyses and reports will be performed when (1) adult immunogenicity data (350 evaluable young adults and 154 evaluable elderly subjects) for Day 57 are available; (2) at least half of core group subjects (at least 3500 evaluable subjects) will be completed Day 85 safety follow up, as EUA application dossier; (3) all immunogenicity data for lot-to lot consistency of Day 57 are available, EUA application dossier; (4) 350 evaluable adolescents completed Day 57 safety follow up, as supplementary dossier for EUA; **(5) immunogenicity and safety data for young and elderly adult subjects receiving 3rd vaccination completed Visit 7, which is 14 days after 3rd vaccination; (6) immunogenicity and safety data for adolescent subjects receiving 3rd vaccination completed Visit 7, which is 14 days after 3rd vaccination.**

The first four analyses and reports will be analysed and drafted by the unblinded statistician, reviewed by the IDMC, and submitted to appropriate regulatory authorities for review if as EUA application dossier or supplementary dossier for EUA.

For the evaluation of safety, immunogenicity, and lot-to-lot consistency, the following endpoints will be included in the first four interim analyses.

- Local reactions, systemic events, unsolicited AEs, and SAEs
- Changes of safety laboratory measures
- Changes of vital signs and physical examinations
- Seroconversion rate of SARS-CoV-2 neutralizing antibody and antigen-specific antibody (Anti-S1-RBD) on Day 57
- Geometric mean titer of SARS-CoV-2 neutralizing antibody and antigen-specific antibody (Anti-S1-RBD) on Day 57
- Geometric mean fold increase in SARS-CoV-2 neutralizing antibody and antigen-specific antibody (Anti-S1-RBD) on Day 57
- Lot consistency by the comparisons of the GMT of SARS-CoV-2 neutralizing titers on Day 57 induced by 3 independent UB-612 vaccine clinical materials. The 95% confidence intervals between groups will be within the margin of 0.5 to 2.

For last two interim analyses (i.e., interim analysis (5) and (6)), the analyses demonstrate the immunogenicity and safety data on the adult and adolescent subjects received 3rd dose of UB-612 including (but not limited to) following endpoints.

- **Local reactions, systemic events, unsolicited AEs, and SAEs after 3rd dose of UB-612**
- **Changes of safety laboratory measures**
- **Changes of vital signs and physical examinations pre/post 3rd dose of UB-612**

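### V-205 builds its 7-day local-reaction summary from e-diary records alone, so a listed reaction entered only in the AE eCRF would be left out; a supplementary either-source rate would guard against this at little cost

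*Supplement*

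**What the plan says.** The V-205 protocol, section 10.5, gives each safety summary a data source. For reactogenicity, "Local reactions and systemic events recorded on e-diary will be summarized by the severity grading scales by study groups". For the other stream, "This analysis applies to all unsolicited adverse events occurring during the study, recorded in AE eCRF". Section 9.5.8 also assigns solicited symptoms to the diary: "Record 7-day solicited symptoms and 14-day skin allergic reaction after vaccination in reactogenicity e-diary".

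The primary endpoint text in 10.5.1 reads "Local reactions for up to 7 days following each dose will be summarized with counts and percentages of participants with the indicated endpoint", with Clopper-Pearson 95% intervals and Fisher's exact test, by study group and vaccination. It names no source and gives no rule for bringing an eCRF entry into this rate. Section 10.9 lists "Local reactions, systemic events, unsolicited AEs, and SAEs" among the contents of the first four interim analyses, some of which are EUA dossiers.

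Sections 9.5.5.1 and 9.5.5.2 define the two classes differently. An event is solicited or unsolicited according to whether its nature or intensity matches the listed expected events. Where it was written down plays no part.

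On V-122, the V-123 protocol (5.5, item 4) describes a recording problem that it puts down to procedure: "some local reactions at the vaccination sites were recorded in the AE eCRF as unsolicited events and were not reported in the subject e-diary". V-122 section 6.2 had a primary endpoint that could absorb such events when related: "Adverse reaction is defined as post-vaccination solicited adverse event, and unsolicited adverse event which is related to study vaccine".

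**The concern.** The analysis rule and the definition can disagree. Injection-site redness above 2.0 cm on day 3 is a solicited local reaction under Table 9-1. If the subject does not enter it and site staff record it in the AE eCRF, 10.5 leaves it out of the local-reaction summary and, at best, it is tabulated as unsolicited.

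V-205 offers a practical route for this. Under 8.1.3, staff call on Day 8 and Day 15 and ask about allergic skin reactions, especially itching and redness, at the injection site or elsewhere. Injection-site itching and redness are both Table 9-1 items. Staff may therefore learn of a reaction with onset inside the 7-day window that the diary does not hold, and nothing shown says how it would reach the local-reaction rate.

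At stake is a primary safety rate, reported per dose against placebo. Any loss lowers it, probably mostly in the vaccine arm, where most local reactions are expected. The severity tables could also be affected, because outside the diary "All AEs, except AEs in e-diary card, will be assessed according to the US NCI Common Terminology Criteria for Adverse Events (CTCAE) 5.0", not Table 9-1.

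**Working it through.** **1. The V-122 precedent.** V-123 section 5.5, item 4, gives related unsolicited AEs in 50.0%, 15.0% and 5.0% of 20 subjects at 10, 30 and 100 µg, which is 10, 3 and 1 subjects. The injection-site events named among them, with exact (Clopper-Pearson) 95% intervals, are:

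| V-122 group | Named event | x/n | Exact 95% CI |
|---|---|---|---|
| 10 µg | injection site reaction | 6/20 = 30.0% | 11.9% to 54.3% |
| 30 µg | injection site rash | 1/20 = 5.0% | 0.1% to 24.9% |
| 100 µg | none (the one related event was constipation) | 0/20 = 0% | 0% to 16.8% |

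The sponsor's 30.0% reproduces. Fisher's exact test of 6/20 against 0/20 gives p = 0.020 (two-sided). The cohorts were enrolled in sequence, so the pattern would fit a recording problem that was settled during V-122, but the documents do not say so. They also speak of some local reactions, so not all six events at 10 µg need have been misrouted.

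**2. Direction.** Let p be the true proportion of vaccinees with a Table 9-1 local reaction and m the share of those subjects whose reaction is in the eCRF only. The e-diary rate is then p × (1 − m), short by p × m. Any m above 0 lowers it.

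**3. Scale, under assumptions.** The documents give neither p nor m for V-205. The core group has 3850 × 6/7 = 3300 vaccinees. For p, take 35% and 80%, the V-122 100 µg rates of any adverse reaction after doses 2 and 1 (V-123 section 5.5, item 1). Because these cover any reaction, both are upper values for local reactions. I added 10% as a lower case. The question is how many reactors must be missing before the upper exact 95% limit of the diary rate falls below p:

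| Assumed p | True reactors | Missing | Share of reactors | Shift in rate |
|---|---|---|---|---|
| 10% | 330 | 34 | 34/330 = 10.3% | 34/3300 = 1.0 points |
| 35% | 1155 | 55 | 55/1155 = 4.8% | 55/3300 = 1.7 points |
| 80% | 2640 | 46 | 46/2640 = 1.7% | 46/3300 = 1.4 points |

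At m = 5%, a true 35% would be reported as 33.3% (0.35 × 0.95) and a true 80% as 76.0% (0.80 × 0.95). The small shares needed mainly reflect the narrow intervals at n = 3300; the shifts themselves are between 1 and 2 points.

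**The case against.** The strongest reply is that this detail belongs in the SAP. Section 10.1 defers full analysis details to that document, none is shown, and reconciling diary with eCRF entries is ordinary SAP content. That would answer a complaint that something is missing. Here, though, the protocol itself states a source rule in 10.5, and the rule does not match its own definitions.

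A second reply is that 9.5.5.2 already makes such a reaction solicited wherever it is recorded, and that 10.5.1 is not limited to the diary. The definition does say that. But 10.5 is the only text on how the summary is built, and it names the e-diary. The definition therefore exposes the mismatch without curing it.

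Several counterpoints stand:

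- Recurrence is not shown. No injection-site event is named at 100 µg, the V-205 dose.
- The instrument was revised. V-205 Table 9-1 drops the optional label on redness and swelling, starts grading above 2.0 cm where V-122 started at 2.5 cm, and gives injection-site itching its own line. Staff also review the diary data at Visit 4.
- Misrouted reactions would very likely still appear, by arm, among unsolicited AEs to Day 57. That is also a primary safety endpoint, with the same interval and test, and goes into the same interim reports.
- Redness or swelling of 2.0 cm or less is below Grade 1 and may properly be unsolicited.

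A reader might infer that V-205 will understate reactogenicity, or that the 30% at 10 µg measures how much will be lost. Neither is supported. The V-122 report gives no diary miss rate, and it concerns local reactions only, so it says nothing about systemic events.

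**Conclusion.** The point holds as a minor one. As written, 10.5 would leave an eCRF-only Table 9-1 reaction out of the 7-day local-reaction rate. The sponsor has reported that kind of misrouting before, the V-205 safety calls provide a route for it, and V-205's local-reaction endpoint lacks the V-122 clause that counted related unsolicited events.

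The effect is conditional on recurrence, and its size cannot be estimated from the documents. With 0 of 20 named at 100 µg and an upper limit of 16.8%, V-122 neither shows nor rules out a loss of the scale in the table. That scale rests on assumed true rates and on 3300 vaccinees. A reader might take the 1.7% and 4.8% thresholds as a sign of fragility, but they correspond to 1.4 and 1.7 percentage points, and nothing in V-205 sets a decision threshold on the local-reaction rate. Misrouted events would most likely be misclassified, not hidden.

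**What to change.** Keep the e-diary local-reaction rate in 10.5 and 10.5.1 as planned. Add to 10.5.1 a supplementary rate, with the same Clopper-Pearson 95% interval and Fisher's exact test: subjects with a Table 9-1 local reaction with onset within 7 days of a dose, recorded in either the e-diary or the AE eCRF.

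Grade eCRF events on Table 9-1 where the recorded information allows. Where it does not, for example because no diameter or effect on activity was captured or the term is non-specific, count the event under any local reaction as grade not available. Show the supplementary rate with and without these events.

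The cost is a preferred-term mapping, a few ungraded events and a combined rate that may be slightly higher than the diary rate. No new data are needed. If the two rates nearly agree, that indicates little was misrouted; if they differ, the report shows by how much.

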10.5.1 Analysis of Primary Safety Endpoint(s)

- Local reactions for up to 7 days following each dose

Local reactions for up to 7 days following each dose will be summarized with counts and percentages of participants with the indicated endpoint and the associated Clopper-Pearson 95% CIs by study group and each vaccination. The group comparison will be assessed by Fisher's exact test. Summary of descriptive statistics by age group will be also provided.

- Systemic events for up to 7 days following each dose

Systemic events for up to 7 days following each dose will be summarized with counts and percentages of participants with the indicated endpoint and the associated Clopper-Pearson 95% CIs by study group and each vaccination. The group comparison will be assessed by Fisher's exact test. Summary of descriptive statistics by age group will be also provided.

- Unsolicited AEs from Day 1 to Day 57

Unsolicited AEs will be presented by descriptive summary statistics (counts, percentages, and associated Clopper-Pearson 95% CIs) with system organ class and preferred term for each study group. The group comparison will be assessed by Fisher's exact test. Summary of descriptive statistics by age group will be also provided.

- MAAEs and SAEs from Day 1 to Day 365

MAAEs and SAEs will be summarized by counts, percentages, and associated Clopper-Pearson 95% CIs for each study group. The group comparison will be assessed by Fisher's exact test. Summary of descriptive statistics by age group will be also provided. **Additionally, the AESIs and ADEs occurred after third vaccination for subjects received three vaccinations will be also summarized separately.**

- AESIs and ADEs from Day 1 to Day 365

AESIs and ADEs will be summarized by counts, percentages, and associated Clopper-Pearson 95% CIs for each study group. The group comparison will be assessed by Fisher's exact test. Summary of descriptive statistics by age group will be also provided. **Additionally, the AESIs and ADEs occurred after third vaccination for subjects received three vaccinations will be also summarized separately.**

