All subjects will come back on Day 197, Visit 5, for immunogenicity persistence check in immunogenicity group and safety check for safety group. **Once subject completes Visit 5, he or she will be unblinded. Subjects received placebo will withdraw from the study and subjects who received UB-612 vaccine will be invited to join the extension study to determine the durability of the immune response and long-term safety after unblinding. Meanwhile, subjects in vaccine group will be encouraged to have a third dose of UB-612. All subjects who received UB-612 vaccine will be followed up for 12 months.**

All subjects will receive safety calls on Day 8, Day 15, Day 22, Day 36, Day 43, Day 64, Day 71, Day 78, Day 85, Day 253, and Day 309 that will serve both to monitor for unsolicited AEs or/and to monitor for symptoms of COVID-19. After Day 57, each week (i.e., every 7 days) the subject will receive a prompt on their smartphone device to regularly surveillance for signs and symptoms of COVID-19 and SAE. **Subjects who received 3rd dose of UB-612 will receive an extra safety call on 7 days post 3rd vaccination.**

If a Grade 3 local reaction, systemic event, or fever are reported in the reactogenicity e-diary, a telephone contact should occur to ascertain further details and determine whether a site visit is clinically indicated. If suspected Grade 4 local reaction systemic event and /or fever is reported in the reactogenicity e-diary, a site visit should occur to confirm whether the event meets the criteria for Grade 4. All subjects were encouraged to contact site staff once they encountered Grade 3/4 AE. Allergic skin reaction should be monitored for 14 days post vaccination and should be contacted regardless of severity.

If a subject experiences a febrile illness associated with respiratory symptoms, he or she is instructed to contact the site immediately. Subjects may utilize a COVID-19 illness e-diary to prompt him/her to report any symptoms.

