9.5.6.5 Definition of Adverse Events of Special Interest (AESI)

Adverse event of special interest (AESI) is further defined in Council for International Organizations of Medical Sciences (CIOMS) VII as [15]:

An adverse event of special interest (serious or non-serious) is one of scientific and medical concern specific to the sponsor's product or specific target disease, for which ongoing monitoring and rapid communication by the investigator to the sponsor could be appropriate. Such an event might require further investigation in order to characterize and understand it. Depending on the nature of the event, rapid communication by the trial sponsor to other parties (e.g., regulators) might also be warranted. Thus AESI should include potential immune medical condition (listed in **Table 9-6**), or any newly identified potential AESI followed through 12 months after participants' final vaccination. Complications of COVID-19 (listed in **Table 9-5**) should be considered and reported as AESIs.

Subjects will be assessed for diagnosis of an AESI at all visit. AESIs include potential ADE medical conditions, AE specific to complications of COVID-19, or other potential AEs that may be determined at any time by regulatory authorities as additional information concerning COVID-19 is obtained. Given the concern for "cytokine storm", an AESI of cytokine release syndrome will be included as an AE specific to COVID-19. Thus AESI included

AESIs specific to complications of potential disease enhancement for COVID-19, also termed ADE (antibody dependent enhancement), will also be monitored (see **Table 9-5**).

Table 9-5 Adverse Events of Special Interest Relevant to COVID-19^a

Body System	Diagnoses ^a
Immunologic	Enhanced disease following immunisation, ^b cytokine release syndrome related to COVID-19 ^c , Multisystem inflammatory syndrome in children (MIS-C)
Respiratory	Acute respiratory distress syndrome (ARDS)
Cardiac	Acute cardiac injury including: 
 • Microangiopathy • Heart failure and cardiogenic shock • Stress cardiomyopathy • Coronary artery disease • Arrhythmia • Myocarditis, pericarditis
Hematologic	Coagulation disorder 
 • Deep vein thrombosis • Pulmonary embolus • Cerebrovascular stroke • Limb ischemia • Hemorrhagic disease • Thrombotic complications
Renal	Acute kidney injury
Gastrointestinal	Liver injury
Neurologic	Guillain-Barré Syndrome, anosmia, ageusia, meningoencephalitis

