10.6.2 Analysis of Secondary Immunogenicity Endpoint(s)

- Seroconversion rate (SCR) of antigen-specific antibody (Anti-S1-RBD) on Day 57

The SCR will be presented as count and percentage in frequency table, and the 95% exact (Clopper-Pearson) confidence interval will be provided as well by study group. Fisher's exact test will be used for the comparison of UB-612 vaccine group and placebo group. Summary of descriptive statistics by age group will be also performed.

- Geometric mean titer (GMT) of SARS-CoV-2 neutralizing antibody on Day 197 and 365

GMT and 2-sided 95% CIs will be provided for each study group. Additionally, the difference between UB-612 vaccine and placebo groups will be analysed by ANCOVA model under log-transform data with baseline level as covariate and effect of study treatment, if appropriate. Summary of descriptive statistics by age group will be also performed.

In addition, the GMT of SARS-CoV-2 neutralizing antibody on Day 365 for subjects received two vaccinations and three vaccinations should be analysed separately. Analysis of GMT of SARS-CoV-2 neutralizing antibody on Day 365 for subjects received third dose of UB-612 will be performed with the Evaluable Booster Population only.

- Geometric mean titer (GMT) of antigen-specific antibody (Anti-S1-RBD) on Day 57, 197, and 365

GMT and 2-sided 95% CIs will be provided for each study group. Additionally, the difference between UB-612 vaccine and placebo groups will be analysed by ANCOVA model under log-transform data with baseline level as covariate and effect of study treatment, if appropriate. Summary of descriptive statistics by age group will be also performed.

In addition, the GMT of Anti-S1-RBD on Day 365 for subjects received two vaccinations and three vaccinations should be analysed separately. Analysis of GMT of Anti-S1-RBD on Day 365 for subjects received three vaccinations will be performed with the Evaluable Booster Population only.

- Geometric mean fold increase in antigen-specific antibody (Anti-S1-RBD) and SARS-CoV-2 neutralizing antibody on Day 57, 197 and 365

GMFI and 2-sided 95% CIs will be provided for each study group. Additionally, the difference between UB-612 vaccine and placebo groups will be analysed by Student's t test under log-transform data. Summary of descriptive statistics by age group will be also performed.

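### V-205 compares MAAEs, SAEs, AESIs and ADEs between arms to Day 365 as crude percentages, although placebo follow-up is planned to stop at Day 197; this can create a false harm signal, mainly for commoner events

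*Supplement*

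**What the plan says.** All references are to the V-205 protocol.

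- **Endpoints and test (10.5.1).** Two of the primary safety endpoints are "MAAEs and SAEs from Day 1 to Day 365" and "AESIs and ADEs from Day 1 to Day 365". For the first, "MAAEs and SAEs will be summarized by counts, percentages, and associated Clopper-Pearson 95% CIs for each study group"; for the second, "AESIs and ADEs will be summarized by counts, percentages, and associated Clopper-Pearson 95% CIs for each study group". Both are compared between study groups by Fisher's exact test. Section 10.7 carries the same analyses over to adolescents.
- **Denominator (10.3).** The Safety Population is everyone who received at least one injection.
- **Follow-up (Synopsis, 7.1, 8.1.8).** Each subject is unblinded on completing Visit 5 (Day 197 ± 15 days). In 7.1, "Subjects received placebo will withdraw from the study"; 8.1.8 lists the withdrawal of placebo subjects as a Visit 5 procedure. Vaccinees are followed for 12 months and encouraged to take a third dose between Day 197 and Day 242. Section 7.3 is softer and only allows placebo subjects to leave.
- **After dose 3 (10.5.1).** Under both bullets the text reads "Additionally, the AESIs and ADEs occurred after third vaccination for subjects received three vaccinations will be also summarized separately". The MAAE/SAE bullet therefore names the wrong events.
- **Day 365 immunogenicity (10.6.2).** Vaccine is compared with placebo by ANCOVA for "Geometric mean titer (GMT) of SARS-CoV-2 neutralizing antibody on Day 197 and 365" (and likewise for anti-S1-RBD), where appropriate, and by a t test for fold increase at the same days, without that qualifier.
- **AESI duration (9.5.6.5).** AESIs are to include "any newly identified potential AESI followed through 12 months after" the final vaccination.

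**The concern.** A proportion of subjects with an event grows with time at risk. If one arm is observed for nearly twice as long, its percentage will be higher even when the underlying risk is identical, and Fisher's test has no means of allowing for that. In this plan the longer-observed arm is the vaccine arm, and its extra time is also open-label and partly follows an additional dose.

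At stake is the reading of two primary safety comparisons in the final report. A difference produced by follow-up length could be reported as vaccine harm, and a genuine difference could not be separated from it. The Day 365 immunogenicity contrasts have a simpler problem: if placebo subjects have gone, there is no placebo sample to compare with.

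**Working it through.** **The plan's own safety figure.** Section 10.2.1 gives the chance of seeing at least one SAE as 1 − (1 − p)^N. For p = 0.01% and N = 3000 this is 1 − 0.9999^3000 = 0.2592, against 25.9% in the plan. All twelve cells of that table reproduce. The table concerns the vaccine arm alone and does not deal with unequal follow-up.

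**Inputs**

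- Arm sizes (10.2): 3850 adults at 6:1 gives 3850 × 6/7 = 3300 vaccine and 550 placebo.
- Time at risk: Day 1 to 365 is 364 days; Day 1 to 197 is 196 days; ratio 364/196 = 1.86.
- Assumptions, because the documents give none of these: the same constant hazard in both arms, complete capture of events, no other loss, and a two-sided 5% level. The 12-month risk p is varied.

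**Formulas.** Daily hazard h = −ln(1 − p)/365. Expected vaccine percentage = 1 − exp(−364h); expected placebo percentage = 1 − exp(−196h). The probability that Fisher's test rejects was then obtained by exact enumeration of both binomial distributions.

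Example, p = 5%: h = 0.051293/365 = 0.0001405 per day; vaccine 1 − exp(−0.05115) = 4.99%; placebo 1 − exp(−0.02754) = 2.72%; ratio 1.84; expected subjects with an event 165 and 14.9.

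| 12-month risk | Vaccine % | Placebo % | False rejection as planned | Both arms cut at Day 197 |
|---|---|---|---|---|
| 0.5% | 0.50 | 0.27 | 1.3% | 2.5% |
| 1% | 1.00 | 0.54 | 9.3% | 3.0% |
| 2% | 1.99 | 1.08 | 27% | 3.6% |
| 5% | 4.99 | 2.72 | 68% | 4.2% |
| 10% | 9.97 | 5.50 | 95% | 4.5% |

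A separate simulation gave about 2% in the first row. From a 1% risk upward, practically every false rejection points towards vaccine harm.

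**Sensitivity of the false rejection rate**

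- Only half of vaccinee events after Day 197 captured: 3.9%, 23% and 46% at risks of 1%, 5% and 10%.
- Half of placebo subjects stay to Day 365: 3.7%, 18% and 36% at the same risks.
- 3000 against 500 subjects: 8%, 63% and 93% at the same risks.
- Adolescents, 330 against 55: 12%, 31% and 45% at risks of 10%, 20% and 30%.
- Person-time rates to Day 365 in place of percentages: 3.3%, 4.1% and 4.7% at risks of 1%, 5% and 20%. This restores the level under a constant hazard, but still mixes blinded two-dose time with open-label three-dose time.

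**Follow-up after dose 3.** Dose 3 at Day 197 leaves 365 − 197 = 168 nominal days; at Day 242 it leaves 365 − 242 = 123. Neither is 12 months.

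**The case against.** Several points on the other side are fair.

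- *A reader might infer that equal risk will look like harm for all four endpoints.* The documents do not support that. They give no event rates, and at a 12-month risk of 0.5% the test rejects 1.3% of the time. COVID-19 complications, which the protocol also calls ADEs, count only with a positive PCR and may be rare. MAAEs are different: section 9.5.6.4 covers any non-routine medical visit, and subjects up to age 85 with stable disease are eligible, so higher rates are plausible.
- *A reader might take it as settled that every placebo subject leaves.* Section 7.3 is permissive and conflicts with the Synopsis, 7.1 and 8.1.8. If some stay, the bias shrinks but remains.
- *Surveillance is passive from Visit 5.* Full capture is therefore optimistic and the larger rejection figures are upper-end. Different ascertainment by period is, however, another reason not to pool the two periods.
- *A reader might infer that events after dose 3 are never separated.* Section 10.9 lists SAEs after the third dose in interim analyses 5 and 6. That reaches only to Visit 7 and does not name MAAEs.
- *No decision rests on these tests.* No alpha or success criterion is stated, section 10.5 frames safety as descriptive, the stopping rules do not use Fisher's test, and the first four interim analyses are tied to Day 57 or Day 85 data. Under equal capture the bias runs against the vaccine. This lowers the severity but does not make the comparison valid.
- *The SAP could deal with it.* No V-205 SAP is shown. The protocol itself fixes the window, denominator and test, so an SAP that follows it inherits the problem.
- *The Day 365 GMT ANCOVA is conditional.* It is, and it would presumably be dropped. The fold-increase t test is unconditional.

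**Conclusion.** The comparison is wrong as written. The Day 1 to Day 365 window does not match the placebo arm's planned exit at Day 197, and nothing in the protocol corrects for this in the MAAE/SAE and AESI/ADE comparisons. Under equal constant hazards, complete capture and no other loss, the vaccine percentage is inflated about 1.8-fold. Whether that becomes a significant false signal depends on how common the event is: unlikely at a 12-month risk of 0.5%, about one in ten at 1%, about two in three at 5% and nearly certain at 10%, with roughly a third to a half of that at 5–10% under half capture or half retention of placebo. The hazards, the event rates and the 5% level are assumptions.

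The supportable conclusion is that the plan can create a false harm signal, chiefly for MAAEs and commoner SAEs. The duplicated sentence, the Day 365 placebo contrasts and the AESI follow-up text are secondary corrections. This should be fixed, but it does not undermine the interim analyses at Day 57 and Day 85.

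**What to change.** 1. In 10.5.1, and for adolescents through 10.7, restrict the between-arm comparison of MAAEs, SAEs, AESIs and ADEs to Day 1 through unblinding at Visit 5. Censor both arms at the earliest of unblinding, dose 3 or exit.
2. Report vaccinee events from Visit 5 to Day 365 descriptively per person-time, split into two-dose and three-dose time, with no placebo contrast.
3. Correct the MAAE/SAE bullet so that its post-dose-3 summary names MAAEs and SAEs.
4. In 10.6.2, delete the Day 365 vaccine-versus-placebo contrasts for GMT and fold increase; keep the separate two-dose and three-dose summaries.
5. Reconcile 7.3 with the Synopsis, 7.1 and 8.1.8 on placebo withdrawal, and reconcile the AESI follow-up text in 9.5.6.5 and the schedule footnotes with the Day 365 end of follow-up.

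The cost is protocol and SAP wording, with no new data. The report would have to state that controlled safety follow-up is about 6.5 months rather than 12, which is what the design provides if placebo subjects leave at Visit 5.
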